2.3 Exploratory Objectives

To assess inflammatory cytokines and markers of T-cell/macrophage activation (i.e. cytokines, sIL-2R, sCD163) as predictive biomarkers.

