13.1.2 Disease Parameters

- Fever
- Splenomegaly (by physical examination or radiographic imaging).
- Cytopenias involving ≥ 2 cell lines
- Ferritin
- Triglycerides
- Fibrinogen
- Soluble IL-2 receptor
- NK cell activity

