13.1.3 Response Criteria

Evaluation of Response

Response	Evaluation of Target Lesions
Complete Response (CR)	Complete normalization of all quantifiable signs and laboratory abnormalities included in the diagnostic criteria for HPS.
Partial Response (PR)	At least a 25% improvement in two or more quantifiable signs/laboratory markers.
Progressive Disease (PD)	At least a 50% worsening in two or more quantifiable signs/laboratory markers.
Stable Disease (SD)	Neither sufficient improvement to qualify for CR/PR, nor sufficient worsening to qualify for PD.

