Plasma will be obtained before treatment and weekly thereafter, and cryopreserved for future corollary studies (e.g. cytokine^{27,28} and soluble CD163 determination³⁴). We will compare cytokine, soluble IL-2R and soluble CD163 levels pre-treatment and post treatment. We seek to correlate change in expression (decrease) with positive response (complete vs. partial vs. stable) to therapy via regression models that appropriately account for the serial correlation of repeated measures within a patient. Inference from these models would be hypothesis generating.

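### The exploratory regression relates the fall in soluble IL-2R to a response category that soluble IL-2R helps define, so its result is biased toward an association

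*Combined protocol and SAP*

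**What the plan says.** Section 2.3 sets the exploratory objective: "To assess inflammatory cytokines and markers of T-cell/macrophage activation (i.e. cytokines, sIL-2R, sCD163) as predictive biomarkers". Section 15.2 (Exploratory) gives two analyses. The first is a before-and-after comparison: "We will compare cytokine, soluble IL-2R and soluble CD163 levels pre-treatment and post treatment". The second is the regression at issue: "We seek to correlate change in expression (decrease) with positive response (complete vs. partial vs. stable) to therapy via regression models", with models that "appropriately account for the serial correlation of repeated measures within a patient". It adds: "Inference from these models would be hypothesis generating". No alpha, model form, response coding or decision rule is given for these models.

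On the response side:

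- Section 13.1.2 lists "Soluble IL-2 receptor" among eight disease parameters, and section 4.1 makes it a diagnostic criterion (above 2400 U/mL).
- Section 13.1.3 defines CR as normalisation of every quantifiable abnormality in the diagnostic criteria, which includes sIL-2R.
- Section 13.1.3 defines PR as "At least a 25% improvement in two or more quantifiable signs/laboratory markers". Any two markers will do, so sIL-2R can be one of them. PD uses the same structure with 50% worsening.
- Section 15.2 (Secondary) repeats the CR and PR definitions.

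Nothing removes sIL-2R from the score when sIL-2R is the marker under study. Soluble CD163 and the cytokines are not in 13.1.2.

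**The concern.** The same analyte stands on both sides of the model. A patient or visit with a 25% fall in sIL-2R is already halfway to PR, and cannot be CR unless sIL-2R is normal. The hypothesis of no association is therefore false by definition, whether or not sIL-2R follows the rest of the disease. The stated aim is to learn whether sIL-2R is informative about response; the model partly reports that sIL-2R is a component of the response score.

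At stake is how the exploratory result for this one marker is read. The hypothesis-generating label warns about imprecision and multiple looks, but it does not remove a structural bias, and more patients would not shrink it. The three kinds of marker are also not examined on equal terms, since only sIL-2R has the built-in link.

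**Working it through.** The plan gives no figure for this analysis, so there is none to reproduce. The check has an exact step and a simulated step. Both make sIL-2R uninformative, that is, independent of every other marker.

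**Inputs from the documents.** 10 patients (15.1); PR and PD rules (13.1.3); eight parameters (13.1.2); weekly efficacy assessment in weeks 1–5 (15.2). The cytopenia item covers three counts (4.1), so up to 8 − 1 + 3 = 10 items could be counted as markers.

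**Assumptions not in the documents.** The number K of quantifiable markers, the marker distributions, the response coding, and a two-sided 5% test (stated in 15.1 for the primary endpoint only).

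**Step 1, exact.** Let each of K independent markers improve by 25% or more with probability p.

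- If sIL-2R improved, PR needs at least one of the other K − 1: P(PR) = 1 − (1 − p)^(K−1).
- If it did not, PR needs at least two of them: P(PR) = 1 − (1 − p)^(K−1) − (K − 1)p(1 − p)^(K−2).

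The gap is (K − 1)p(1 − p)^(K−2), the chance that exactly one other marker improved. With p = 0.3:

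| K | sIL-2R improved | Not improved | Gap |
|---|---|---|---|
| 5 | 1 − 0.7^4 = 0.76 | 0.76 − 4(0.3)(0.7^3) = 0.35 | 0.41 |
| 8 | 1 − 0.7^7 = 0.92 | 0.92 − 7(0.3)(0.7^6) = 0.67 | 0.25 |

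With sIL-2R left out of the score, P(PR) no longer depends on sIL-2R and the gap is zero.

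**Step 2, simulated rejection rates** (10 patients, PD excluded, nominal 5%).

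| Coding and model | K | As written | sIL-2R left out |
|---|---|---|---|
| One assessment, linear regression | 4, 5, 8 | 4.3–15.8% | 3.3–6.0% |
| Best response, mixed model | 4, 5, 8 | 4.9–10.7% | 2.8–7.0% |
| Each of 5 visits, mixed model | 4–5 | 16–51% | 2.7–7.3% (all K) |
| Each of 5 visits, mixed model | 8 | 7–9% | as above |

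These rows assume mean log changes of 0 to −1 (one assessment) or 0 to −0.5 (five visits), SDs of 0.4–0.8 or 0.4–0.6, correlation among the other markers of 0 or 0.5, and an intraclass correlation of 0.5. There were 1000 runs per scenario for one assessment and 300 for five visits, where one Monte Carlo standard error is up to about 3 points and some fits gave convergence warnings. Ranges cover scenarios in which at least half the simulated trials could be analysed. The mean correlation between sIL-2R change and response was about −0.1 to −0.3 as written, and −0.03 to +0.03 with sIL-2R left out.

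A second simulation used visit-level PR against SD, between- and within-patient SDs of 0.35 and 0.25 on the log scale, correlation 0 or 0.5 among the other markers, and a mean sIL-2R fall of 0% or 25%:

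- Known variances: 13.6–37.9% with 5 markers and 7.9–22.8% with 7, against 4.5–5.7% with sIL-2R left out. Responder visits showed a spurious extra sIL-2R fall of about 8–24%.
- Known variances, more markers: about 7–17% with 8 and about 4–10% with 10.
- Estimated variances, 7 markers: 5–21%, against 2–4% with sIL-2R left out.

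**Step 3, sample size.** With one assessment per patient, rejection for the uninformative marker reached as much as 63% at n = 50. The link does not fade with more data.

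**The case against.** The case for leaving the text alone has several parts.

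- *Rejection is not assured.* A reader might infer that the model must reject no association. It need not: the null is false by construction, but at n = 10 most simulated trials do not reject, and no setting came near 100%. This stands.
- *The large rates need particular choices.* They come from few markers and visit-level scoring, and some assume known variances. The summary measure that 15.2 defines is best overall response, where the rate is 4.9–10.7%. With 10 markers the visit-level rate is close to nominal. This stands. Against it, the models are specified for repeated measures and response is assessed weekly, so visit-level scoring is a natural reading.
- *The CR level was not simulated in full.* The second simulation compared PR with SD only, not the three-level contrast. This limits the figures, not the logic, since CR also requires sIL-2R to be normal.
- *Two assays may be involved.* Section 11.2 measures sIL-2R by ELISA in patient plasma, and the calendar in 12.2 lists clinical sIL-2R and the research draw on separate rows. If response uses one and the model the other, assay error would weaken the link without removing it.
- *No harmful decision is written down.* A reader might infer that the plan will rank sIL-2R above soluble CD163 or interferon-gamma, or carry it forward. The documents contain no ranking, selection or carry-forward rule, so that inference is not supported.
- *The pre/post comparison is not circular.* It is within patient and does not involve response. This stands.

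What remains is that sIL-2R helps define the outcome it is related to, and the plan has no rule to deal with this.

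**Conclusion.** The point holds in a limited form. The overlap is certain from sections 4.1, 13.1.2, 13.1.3 and 15.2, and it biases the sIL-2R result toward an association; this is a rule as written, not a missing detail. Its size is uncertain. Under a nominal 5% test, the false-positive rate for an uninformative sIL-2R runs from about nominal to roughly 10–15% with best-response or single-assessment coding. With visit-level coding it runs from about 5% (10 markers) to 40–50% (4–5 markers). The estimated-variance fit with 7 markers gives 5–21%. All of these rest on assumed marker distributions, and on a marker count and response coding that the plan leaves open.

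The consequence is confined to one marker in an exploratory objective declared hypothesis generating. The 2-month survival endpoint, the 4-of-10 rule, the secondary response rate, PFS, OS and safety are unaffected, as are the soluble CD163 and cytokine models.

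**What to change.** Add to 15.2 (Exploratory): *For the regression of soluble IL-2R on response, CR/PR/SD will be re-scored under 13.1.3 without soluble IL-2R; any other biomarker that is also a 13.1.2 parameter will be handled the same way.* Keep the full 13.1.3 score for the secondary response rate and for the soluble CD163 and cytokine models. Leave the pre/post comparison of sIL-2R levels as it is.

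Seven of the eight parameters remain, so the 13.1.3 rules can still be applied. The data are already scheduled, so no samples or visits are added. The price is that a few patients whose PR depends on sIL-2R become SD in this one analysis, and the sIL-2R association will look weaker. Some other categories may also shift; for example, a patient with everything normal except sIL-2R moves from PR to CR.

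Relating sIL-2R to an outcome that does not contain it, such as 2-month survival, or reporting sIL-2R descriptively, would also avoid the overlap. Re-scoring stays closest to the question the plan asks.

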13. MEASUREMENT OF EFFECT

13.1 Response evaluation

13.1.1 Definitions

Evaluable for toxicity. All patients will be evaluable for toxicity from the time of their first treatment with Ruxolitinib.

Evaluable for objective response. Only those patients who received at least 7 days of therapy, and have had their disease re-evaluated will be considered evaluable for response. These patients will have their response classified according to the definitions stated below.

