15.2 Analyses

Primary:

The primary analysis is the count of patients alive after 2 months since study entry. If 4 or more patients are alive at the 2 months assessment, the null hypothesis of a 15% survival probability at 2 months will be rejected in favor of our alternative hypothesis of a 60% survival probability. Ninety-five percent confidence intervals will be constructed based upon the exact binomial confidence interval. No loss-to-follow-up or censoring is expected prior to the study's primary endpoint assessment.

Secondary:

There are no formal response criteria for secondary HPS. Therefore, efficacy assessments (including appropriate laboratory studies) will be performed weekly (weeks 1-5), and every two weeks (weeks 6-12), and monthly (after 12 weeks), and responses determined as previously reported in a retrospective study.⁸ Briefly, a complete response is defined as

complete normalization of all quantifiable symptoms and laboratory abnormalities (described in the diagnostic criteria for HPS, above). A partial response is defined as at least a 25% improvement in two or more quantifiable symptoms/laboratory markers following the initiation of treatment. The best overall response is the best response recorded from the start of the treatment until disease progression/recurrence

Follow-up time will be calculated from the first administration of ruxolitinib, until death for OS or until disease-progression or death for PFS. Patients lost to follow-up will be censored on the date of their last known clinical assessment. Specifically for DOR, only patients having at least a PR to therapy are evaluable. Duration will be calculated from the date of the determination of partial response or better until the date of progression, death, or additional non-protocol therapy. Again, for patients lost to follow-up, duration will be censored at the time of last clinical assessment. The count and percentage of the number having an objective response (CR, CRu, or PR) will be reported along with confidence intervals. Product-limit estimates of Kaplan and Meier will be used to estimate OS, PFS, and DOR. The likelihood of loss to follow-up is expected to be extremely low.

Exploratory:

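### The exploratory biomarker model scores response as complete, partial or stable only, so patients scored as progressive disease have no outcome level (minor)

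*Combined protocol and SAP*

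**What the plan says.** The exploratory objective (Section 2.3) is to assess cytokines, sIL-2R and sCD163 "as predictive biomarkers". Section 15.2 (Exploratory) plans two analyses.

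- A before/after comparison, not split by response: "We will compare cytokine, soluble IL-2R and soluble CD163 levels pre-treatment and post treatment".
- A response model, intended to "correlate change in expression (decrease) with positive response (complete vs. partial vs. stable) to therapy via regression models", allowing for repeated measures within a patient. Section 15.2 calls inference from these models hypothesis generating.

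The response scale is set elsewhere. Section 13.1.3 has four categories: CR, PR, SD and PD, with PD defined as "At least a 50% worsening in two or more quantifiable signs/laboratory markers". Section 13.1.1 limits who receives a category: "Only those patients who received at least 7 days of therapy, and have had their disease re-evaluated will be considered evaluable for response". Section 15.2 (Secondary) adds: "The best overall response is the best response recorded from the start of the treatment until disease progression/recurrence". The exploratory text does not say whether the model uses this best response or the response at each visit.

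Research blood is drawn before treatment and every 7 days (±2) thereafter (Section 11.3). Under the Section 12.2 calendar, draws stop 14 days after a CR or after 5 weeks of treatment, whichever comes first.

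**The concern.** A marker proposed as predictive of benefit should be tested against lack of benefit. As written, the worst outcome level is stable disease, which the text itself places under positive response. A patient scored as PD may have a baseline sample and weekly samples but cannot enter the model. The same holds for a patient with a post-baseline sample who dies or stops before re-evaluation.

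Cutting off the bad end of an outcome narrows its range, which usually weakens the observed association, and it removes patients from a set of only 10. The before/after comparison does not recover the contrast because it ignores response. No planned analysis relates the markers to survival or PFS.

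A smaller point concerns the same outcome. Section 13.1.2 lists "Soluble IL-2 receptor" as a response parameter, and sIL-2R is also one of the markers tested against response. Part of that association arises by construction.

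**Working it through.** The plan gives no power, effect size or sample size for this model, so there is no figure to reproduce. The check has four steps.

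**1. Who has an outcome level and a change value**

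| Patient | Level in the model as written | Marker change available |
|---|---|---|
| Scored CR, PR or SD | Yes | Yes |
| SD or better, later progresses or dies (best overall response used) | Yes | Yes |
| Scored PD | No | Yes, if sampled after baseline |
| Sampled after baseline, dies or stops before re-evaluation | No | Yes |
| Dies or stops before the first weekly draw (about day 7 ± 2) | No | No |

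The category list is the cause of exclusion in the third and fourth rows only. The fourth row is probably small, because the weekly draw and the weekly disease assessments share a visit. In the fifth row no recoding helps: a model of change needs a change.

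**2. Context from the plan's survival rates (Section 15)**

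Expected deaths by two months among 10 patients = 10 × (1 − S):
- S = 0.60: 10 × 0.40 = 4.0
- S = 0.15: 10 × 0.85 = 8.5

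Assuming exponential survival over 61 days, deaths before day 7 = 10 × (1 − S^(7/61)):
- S = 0.60: about 0.6
- S = 0.15: about 2.0

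These are deaths, not counts of PD or unevaluable patients. The documents do not allow the latter to be computed. The 0.6 of 10 is the basis for the 6% without a post-baseline sample in step 3.

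**3. Illustration of the loss**

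Assumptions, none of them from the documents except n:
- n = 10, with one marker change per patient.
- Marker change and latent outcome are bivariate normal with correlation 0.7.
- The latent outcome is cut into a failure category of the stated share and three equal categories for SD, PR and CR.
- The worst 6% have no post-baseline sample, except in the last row.
- Spearman test, two-sided 5%.

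| Failure share | Power, failures with a sample kept | Power, CR/PR/SD only |
|---|---|---|
| 40% | about 44% | about 15% |
| 20% | about 45% | about 30% |
| 10% | about 44% | about 39% |
| 20%, none sampled after baseline | about 29% | about 29% |

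A rerun for this write-up agreed to within about one percentage point. In the 40% case the three-level model keeps 10 × 0.60 = 6 patients on average, against 10 × 0.94 = 9.4. Mean Spearman correlation is 0.43 against 0.58.

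**4. sIL-2R overlap**

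Suppose there is no drug effect, 5 or 8 independent markers, log-SD 0.3 for each change, and PR means at least two markers down by 25% or more. A 25% fall in sIL-2R then appears in 30% to 44% of patients called PR and in 8% to 10% of the others. Independence and the SD are assumed, so this shows that the overlap can matter, not how much it will.

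**The case against.** The strongest case against is that nothing turns on this analysis. It is exploratory, no power is claimed for it, and no decision rests on it. OS and PFS capture the failures, and progressors with samples stay in the before/after comparison. That stands, and it sets the severity. It does not explain why a defined response category is left out of a model whose purpose is prediction.

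Three stronger readings are tempting, and the documents do not support them.

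- **A reader might infer that everyone who progresses, dies or stops early is lost because of the category list.** Patients without a post-baseline draw are missing because they have no change value. Under best overall response, a patient who reaches SD or better and later progresses stays in.
- **A reader might infer that about 4 of 10 patients drop out, from the 60% survival alternative.** Death by two months is not the same as PD or being unevaluable. PR needs only a 25% improvement in two markers and response is assessed weekly, so some who die by month 2 may already have a scored response.
- **A reader might infer a fall in power from about 53% to 15%.** At 40% failures, the 53% gives all 10 patients a marker change, including those who could not have one. The simulated test is also simpler than the planned repeated-measures regression.

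The sIL-2R point concerns one marker of several. Cytokines and sCD163 are not response parameters, and rescoring response creates a definition that differs from the secondary endpoint. That is why a sensitivity analysis is enough.

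**Conclusion.** The point holds in a limited form and is minor. Followed as written, the model excludes patients whose scored response is PD and sampled patients who die or stop before re-evaluation, so it estimates the marker-response association on a truncated outcome.

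The size cannot be fixed from the documents. Under the stated assumptions the loss runs from nothing (no failure has a post-baseline sample), through about 5 percentage points of power (10% failures), to about 29 points (40% failures). These figures illustrate direction and sensitivity and are not properties of the planned model. Even with failures kept, power in the illustration stays below one half, so the gain is a more relevant contrast rather than an adequately powered one. The two-month survival analysis and its decision rule are unaffected.

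**What to change.** In Section 15.2 (Exploratory):

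1. Replace the three-level list with the ordered outcome CR > PR > SD > PD, and place patients with a post-baseline sample who die or stop before re-evaluation in the worst level. Alternatively, compare CR/PR with all other treated patients who have a post-baseline sample.
2. State that the outcome is best overall response as defined in Section 15.2.
3. Relate baseline marker level to two-month survival in all treated patients, so that those with only a baseline sample contribute.
4. For sIL-2R only, add a sensitivity analysis that scores response without the sIL-2R component.

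The cost is wording and a little programming. Samples, response assessments and survival status are already collected. There are two downsides: early death or stopping is pooled with PD, which mixes different kinds of failure, and one marker needs a second response score. The change should be made before outcomes are reviewed, because with 10 patients the placement of a few failures could decide the result.

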17. APPENDIX A

POTENTIAL CYP3A4 INTERACTIONS

CYP3A4 Substrates

Albuterol	Dihydroergotamine	Isosorbide	Progesterone
Alfentanil	Diltiazem	Isosorbide, dinitrate	Quetiapine
Alprazolam	Disopyramide	Isosorbide mononitrate	Quinidine
Amiodarone	Docetaxel	Isradipine	Rabeprazole
Amlodipine	Doxepin	Itraconazole	Ranolazine
Amprenavir	Doxorubicin	Ketamine	Repaglinide
Aprepitant	Doxycycline	Ketoconazole	Rifabutin
Aripiprazole	Efavirenz	Lansoprazole	Ritonavir
Atazanavir	Eletriptan	Letrozole	Salmeterol
Atorvastatin	Enalapril	Levonorgestrel	Saquinavir
Benzphetamine	Eplerenone	Lidocaine	Sibutramine
Bisoprolol	Ergoloid mesylates	Losartan	Sildenafil
Bortezomib	Ergonovine	Lovastatin	Simvastatin
Bosentan	Ergotamine	Medroxyprogesterone	Sirolimus
Bromazepam	Erythromycin	Mefloquine	Spiramycin
Bromocriptine	Escitalopram	Mestranol	Sufentanil
Budesonide	Estradiol	Methadone	Sunitinib
Buprenorphine	Estrogens,	Methylergonovine	Tacrolimus
Buspirone	conj., synthetic	Methysergide	Tamoxifen
Busulfan	Estrogens,	Miconazole	Tamsulosin
Carbamazepine	conj., equine	Midazolam	Telithromycin
Cerivastatin	Estrogens,	Miglustat	Teniposide
Chlordiazepoxide	conj., esterified	Mirtazapine	Tetracycline
Chloroquine	Estrone	Modafinil	Theophylline
Chlorpheniramine	Estropipate	Montelukast	Tiagabine
Cilostazol	Ethinyl estradiol	Moricizine	Ticlopidine
Cisapride	Ethosuximide	Nateglinide	Tipranavir
Citalopram	Etoposide	Nefazodone	Tolterodine
Clarithromycin	Exemastane	Nelfinavir	Toremifene
Clobazam	Felbamate	Nevirapine	Trazodone
Clonazepam	Felodipine	Nicardipine	Triazolam
Clorazepate	Fentanyl	Nifedipine	Trimethoprim
Cocaine	Flurazepam	Nimodipine	Trimipramine
Colchicine	Flutamide	Nisoldipine	Troleandomycin
Conivaptan	Fluticasone	Norethindrone	Vardenafil
Cyclophosphamide	Fosamprenavir	Norgestrel	Venlafaxine
Cyclosporine	Gefitinib	Ondansetron	Verapamil
Dantrolene	Haloperidol	Paclitaxel	Vinblastine
Dapsone	Ifosfamide	Pergolide	Vincristine
Dasatinib (1)	Imatinib	Phencyclidine	Vinorelbine
Delviridine	Indinavir	Pimozide	Zolpidem
Diazepam	Irinotecan	Pipotiazine	Zonisamide
		Primaquine	Zopiclone

